2.1.2 Secondary Objectives

- To establish that a multi-arm trial strategy is an efficient way of screening drugs in SPMS and can become the template for future work
- To explore any anti-inflammatory drug activity using the count of new and enlarging T2 lesions

- Examining for evidence of pseudo-atrophy by MRI (to ensure reliability of the primary outcome measure)
- To examine the clinical effect of neuroprotection as measured by clinician (EDSS, MSFC, SDMT, SLCVA, relapse rate) and patient reported outcome measures (MSIS29v2, MSWSv2, Pain [NPRS, BPI and NPS]) and Fatigue [NF])
- To collect basic health economic data (ED-5D) to inform future phase III trials

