A variety of attempts have been made to replace EDSS with alternative scoring methods such as the MSFC score,⁶³ which comprises quantitative tests of walking, arm function and a simple cognitive task (PASAT), with each component converted to a Z-score; or even one of the components of the MSFC, the Timed 25 Foot Walk. This will be acquired, along with a suggested refinement for the PASAT, the SDMT,⁶⁴ which measures information processing speed for visually presented stimuli, but is self-paced, with at least equal reliability and sensitivity to the presence of worsening cognitive impairment. The recommended SLCVA correlates well with diseases phase (RRMS vs SPMS), retinal nerve fibre layer (RNFL) thinning on Optical Coherence Tomography, patient reported visual impairment and MRI burden.⁶⁵ Whilst SPMS is generally non-relapsing, occasional relapses can occur, and will be recorded. Two commonly used Patient Reported Outcome Measures (PROMS) in MS trials, are the MS Impact Scale-29 v2 (MSIS29v2),66 which measures physical and psychological well-being over the previous 2 weeks, and the MS Walking Scale v2 (MSWSv2),67 which looks at walking. The Numerical Pain Rating Score (NPRS), 68 the Brief Pain Inventory (BPI),69 the Neuropathic Pain Scale (NPS),⁷⁰ and the Neurological Fatigue Index (NFI)⁷¹ will assess pain and fatigue respectively. It also seems appropriate to capture some simple health economic metrics for future phase III trials. Therefore the EuroQoL (EQ-5D) will be collected in the total cohort.72

In summary the clinical secondary outcome measures are:

- Expanded Disability Status Scale (EDSS)
- Timed 25 Foot Walk (T25FW)
- 9 Hole Peg Test (9HPT)
- Paced Auditory Serial Addition Test (PASAT)
- MS Functional Composite score comprising of the following:
 - Timed 25 Foot Walk (T25FW)
 - 9 Hole Peg Test (9HPT)
 - Paced Auditory Serial Addition Test (PASAT)
- Symbol Digit Modalities Test (SDMT)
- Sloan Low contrast visual acuity (SLCVA)
- Relapse rate
- Multiple Sclerosis Impact Scale v2 (MSIS29v2)
- Multiple Sclerosis Walking Scale v2 (MSWSv2)
- Brief Pain Inventory (BPI)
- Numerical Pain Rating Score (NPRS)
- Neuropathic Pain Scale (NPS)
- Neurological Fatigue Index (NFI)
- Sponsor No.12/0219 v7

• Health economics (EQ-5D)

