7.2 STUDY ASSESSMENTS

The Schedule of Events below provides details of all assessments.

	MS-SMAF	RT Sche	dule of E	Events										
MC CMADTClinic Visit Number	0		1	2	3	4	5	6	7	8		9		
Version 6 5 th October 2017 Visit Type	Screening	Baseline MRI Visit	Baseline	Titration							End of Study MRI {must be done while on IMP]	End of study	Follow- up (Tel.)	Unscheduled visit
			Wk 0	Wk 4	Wk 8	Wk 12	Wk 24	Wk 36	Wk 48	Wk 72	Wk 96	Wk 96	Wk 100	
Window				+/- 1wks	+/- 1wks	+/- 1wks	+/- 2wks	+/- 2wks	+/- 2wks	+/- 2wks		+2 weeks	+/- 4 days	
Informed consent	x													
Inclusion/exclusion criteria review	x		х											
Demography	x													
Review of medical and MS History	x													x
EDSS - Review [Treating physician]	x													
EDSS – [Assessing physician]			х						х			x		
Physical Examination	x								x			x		x
Vital signs	x								x			x		x
Safety bloods CR&E, FBC, LFT (inc.GammaGT)†	x			x	x	x	x	x	x	x		x		xd
Urine pregnancy test†		ха	ха				xa,e					xa,e		
Book MRI	x					х				х				
Core MRI		xb					х				xc			
Compliance assessment				x	x	х	х	x	х	х		x		
Relapse assessment (count / grade)	x		x	x	x	х	x	x	x	x		x		x
Adverse events			х	x	x	x	x	x	x	x		x	x	x
Concomitant Medication	x		х	x	x	х	x	х	х	x		x		x
Randomisation			х											
Prescription issued			xf	x	x	х	х	x	х	х				
Drug up-titration				x										
Follow-up													х	
Blinding Questionnaire												x		
MSFC (9HTP, 25TFW, PASAT)			х						х			x		
SDMT			х						х			x		
SLCVA			х						x			x		

MSIS-29v2		x			x		х	
MSWSv2		x			х		x	
NFI - PRO		x			х		x	
NPRS, NPS and BPI		х			х		х	
EQ-5D		х			х		х	
BDI	х							

Clinic Visit Number	0		1	2	3	4	5	6	7	8		9		
Visit Type	Screening	Baseline MRI Visit	Baseline	Titration							End of study MRI	End of study	Follow- up (Tel.)	Unsheduled visit
			Wk 0	Wk 4	Wk 8	Wk 12	Wk 24	Wk 36	Wk 48	Wk 72		Wk 96	Wk 100	
Window				+/- 1wks	+/- 1wks	+/- 1wks	+/- 2wks	+/- 2wks	+/- 2wks	+/- 2wks		+2wks	+/- 4 days	
OCT (subgroup)			xg									xc		
CSF Neurofilament/lymphocytes (subgroup) Lumbar puncture††			xg						x			хс		
CSF Neurofilament/lymphocytes (subgroup) Blood & urine samples††			xg			x	x		x	x		хс		
Advanced MRI (subgroup)		x										х		x
Staff Present														x
Treating Neurologist	у								у			у		x
Independent Assessing Neurologist			У						у			у		
Study Nurse	у		у	у	У	у	У	у	у	у		у		xd

Notes				
a= must occur prior to MRI and at baseline visit, within 1 week (-7 days) Applies to WOCBP. Repeat testing will be dependent on timing of assessments.				

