9.2.3 Secondary MRI Outcome

9.2.3.1 Pseudoatrophy:

Using the same methods as for the primary MRI outcome, the mean difference in PBVC from baseline to 6 months between the placebo group and each of the active treatment groups will also be assessed. If the reduction in PBVC is significantly greater in any treatment group a secondary analysis will compare PBVC from week 24 to week 96 between that treatment group and the placebo group using normal linear modelling as in section 9.2.2. As this is an exploratory secondary analysis, no formal adjustment for multiplicity will be made.

9.2.3.2 Counts of new and enlarging T2 lesions:

Each active treatment group will be compared with placebo in terms of the number of new and enlarging T2 lesions between the baseline and 96 week MRI. Over-dispersed Poisson regression models will be used to estimate the percentage difference in new/enlarging lesion count after adjusting for baseline T2 lesion volume and the minimisation variables: age, gender, treatment centre and baseline EDSS.

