9.2.4 Clinical Secondary Outcome Measures

When the change over time in continuous outcomes (EDSS, 9 hole peg test, PASAT, MS functional composite score, Symbol Digit Modalities Test (SDMT), Sloan Low contrast visual acuity (SLCVA), Multiple Sclerosis Impact Scale v2 (MSIS29), Multiple Sclerosis Walking Scale v2 (MSWS), NFI, NPRS, BPI, NPS and health-related quality of life (EQ-5D)) is found to be reasonably normally distributed, perhaps following transformation, these will be compared for active treatments and the placebo groups using normal linear models as in section 9.2.2. If normality cannot be assumed, non-parametric comparison tests will be used. Cox proportional hazard models (adjusting for the minimisation variables) will be used for time to first relapse, timed 25 foot walk and time to progress to a given EDSS score, with the difference between each active treatment and placebo being expressed in terms of a hazard ratio. In exploratory analyses, additional statistical modelling will assess whether composites of imaging and disability measures can be used to predict temporal evolution of SPMS and response to treatment.

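### Relapse rate is a named secondary outcome, but the only relapse analysis the protocol specifies is time to first relapse, which gives a hazard ratio and not a rate ratio

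*Protocol*

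**What the plan says.** Relapse rate appears as a secondary measure in four places: the synopsis objectives, the synopsis list of secondary outcomes, section 2.1.2, where effect is to be measured by "clinician (EDSS, MSFC, SDMT, SLCVA, relapse rate", and section 2.2.2.2, in the list introduced by "In summary the clinical secondary outcome measures are".

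On expected frequency, section 2.2.2.2 says only this: "Whilst SPMS is generally non-relapsing, occasional relapses can occur, and will be recorded". No numerical rate is given anywhere for the trial population.

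On data, the schedule in section 7.2 has a row "Relapse assessment (count / grade", ticked at screening, at every clinic visit from baseline to week 96 and at unscheduled visits. Section 10.4.6.1 collates relapses separately from adverse events.

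On analysis, section 9.2.4 states: "Cox proportional hazard models (adjusting for the minimisation variables) will be used for time to first relapse". The same sentence ends "with the difference between each active treatment and placebo being expressed in terms of a hazard ratio". Relapse is not in that section's list of continuous outcomes. The only count model in the protocol is in section 9.2.3.2, for MRI lesions: "Over-dispersed Poisson regression models will be used to estimate the percentage difference in new/enlarging lesion count".

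**The concern.** A rate counts every relapse over the time each participant was observed. Time to first relapse stops at the first event. These are different quantities with different effect measures, and the protocol names one and specifies a method for the other.

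This is more than a detail deferred to the SAP. Section 9.2.6 leaves derived variables, missing data, sensitivity analyses and assumption checks to the SAP, but section 9.2.4 has already chosen the relapse model. A SAP that follows 9.2.4 literally would not compare relapse rates. A SAP that compares rates would be adding to the stated method. If the two passages are not reconciled before unblinding, the choice between a hazard ratio and a rate ratio stays open when the results are seen.

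**Working it through.** **Text check.** The protocol has no relapse figure to reproduce. Set side by side, the four places that name the outcome say rate, and the one place that specifies an analysis says first event and hazard ratio. Nothing in the protocol plans a relapse count model, an annualised rate or a rate ratio.

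**Inputs.** 110 per arm (section 9.1.1) and 96 weeks of follow-up (section 3), so T = 96 × 7 / 365.25 = 1.84 years. The relapse rate r is assumed at 0.05 to 0.3 per year. Between-patient variation is assumed as gamma with variance k = 0 (Poisson), 1 or 2. No dropout.

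**Share of relapses not used.** Mean relapses per person μ = rT. P(at least one) = 1 − exp(−μ) when k = 0, and 1 − (1 + kμ)^(−1/k) otherwise. Share ignored = 1 − P/μ.

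| r per year | μ | Relapses per arm | First relapses, k = 0 / 1 / 2 | Ignored, k = 0 to k = 2 |
|---|---|---|---|---|
| 0.05 | 0.092 | 10.1 | 9.7 / 9.3 / 8.9 | 4.5% to 12.0% |
| 0.1 | 0.184 | 20.2 | 18.5 / 17.1 / 16.0 | 8.7% to 21.2% |
| 0.2 | 0.368 | 40.5 | 33.9 / 29.6 / 26.5 | 16.3% to 34.5% |
| 0.3 | 0.552 | 60.7 | 46.7 / 39.1 / 34.2 | 23.1% to 43.7% |

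**Does the hazard ratio equal the rate ratio?** With k = 0 and a constant rate, yes. With k > 0, the population cumulative hazard of a first relapse by T is ln(1 + kμ)/k. For an assumed true rate ratio of 0.54, the ratio of cumulative hazards at 96 weeks is ln(1 + 0.54kμ) / ln(1 + kμ):

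- r = 0.1, k = 1: ln(1.0994)/ln(1.1840) = 0.56. With k = 2: ln(1.1987)/ln(1.3680) = 0.58.
- r = 0.3, k = 1: ln(1.2981)/ln(1.5520) = 0.59. With k = 2: ln(1.5961)/ln(2.1039) = 0.63.

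So the first-event measure is pulled modestly towards 1, and more so at higher rates.

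**Is power lost?** One active arm against placebo, rate ratio 0.54, two-sided 5%, k = 0, with μ0 and μ1 = 0.54μ0 the means in the two arms:

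- First event: expected events D = 110[2 − exp(−μ0) − exp(−μ1)], power = Φ(|ln 0.54|·√D/2 − 1.96).
- Counts: SE = √[1/(110μ0) + 1/(110μ1)], power = Φ(|ln 0.54|/SE − 1.96).

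| r per year | First event | Counts |
|---|---|---|
| 0.1 | 38.1% | 37.5% |
| 0.2 | 61.7% | 64.1% |
| 0.3 | 76.1% | 81.1% |

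A simulation of the same design with k from 0 to 2 compared a log-rank test of first relapse with a quasi-Poisson test of counts. Counts gave no gain at 0.05 per year, about −1 to +2 points at 0.1, and about 3 to 14 points at 0.2 to 0.3.

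**The case against.** The strongest reply is that little harm follows. Section 9.2.4 does not say the Cox model is the sole relapse summary, and the unseen SAP may add a rate. Under a homogeneous constant-rate process the two effect measures coincide. Relapse is one of about fifteen clinical secondary measures, and no power claim rests on it. All of this stands and limits the size of the point. It does not remove it, because the protocol still specifies no comparison of the quantity it names, and it nowhere assumes homogeneity.

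Three stronger readings are tempting, and the documents do not support them.

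- *That the trial cannot report relapse rate.* It can. Counts are collected at every clinic visit, so a rate per arm is available. What is missing is a specified comparison of rates.
- *That the fluoxetine result in section 1.2.2.1 (0.54, 95% CI 0.29 to 0.98) makes the rate the relevant comparison here.* That study had 40 patients, 10% of them with SPMS. This trial excludes relapsing-remitting MS and any relapse within three months of baseline. Section 2.2.2.1 gives the search for an unanticipated immunomodulatory effect to T2 lesions. The 0.54 serves above only as an assumed effect for the power illustration.
- *That scarce relapses make discarding repeats costly.* The arithmetic runs the other way: with few relapses almost all are first relapses, and a count analysis gains nothing appreciable.

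**Conclusion.** The mismatch between outcome and analysis is real but minor. As the protocol stands, a secondary outcome labelled as a rate would be compared through a hazard ratio for the first event, and the two agree only under a condition the protocol does not state.

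The size rests wholly on assumed relapse rates, since the protocol describes relapses only as occasional, and on full follow-up of 110 per arm, although section 9.1.1 expects 10% to drop out. If the true rate is 0.1 per year or lower, the practical effect is mainly one of labelling. At 0.2 to 0.3 per year the loss of power and the attenuation become noticeable. The primary PBVC analysis is untouched.

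**What to change.** In section 9.2.4, add one sentence: each participant's relapse count will be analysed with an over-dispersed Poisson or negative binomial model, with log follow-up time as offset and the minimisation variables as covariates, and reported as a rate ratio for each drug against placebo. Keep the Cox model of time to first relapse as supportive. The offset also accommodates participants who leave early.

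At minimum, rename the outcome as time to first relapse in the synopsis objectives, the synopsis outcome list and sections 2.1.2 and 2.2.2.2. This also removes the inconsistency, at the price of giving up the rate comparison.

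The cost is one sentence and one extra model of a kind already planned for T2 lesions, or a change of label in four places. No new data are needed. Settle it before unblinding.

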9.2.5 Interim analyses

Unblinded safety data will be monitored by a Data Monitoring Committee to ensure the ongoing safety of patients in the study. No formal interim analyses will be conducted.

9.2.6 Statistical Analysis Plan

A full statistical analysis plan (SAP) will prepared which will include details of methods for calculating derived variables, methods for handling missing data and withdrawals, any sensitivity analyses and approaches to testing the assumptions in the statistical analyses. The SAP will summarise the plan for validation of the statistical analysis. The SAP will list the tables, data listings and figures to be reported.

10 ADVERSE EVENTS

10.1 **DEFINITIONS**

Term	Definition
Adverse Event (AE)	Any untoward medical occurrence in a patient or clinical trial subject administered a medicinal product and which does not necessarily have a causal relationship with this treatment.
Adverse Reaction (AR)	Any untoward and unintended response in a subject to an investigational medicinal product which is related to any dose administered to that subject.

	This includes medication errors, uses outside of protocol (including misuse and abuse of product)
Serious adverse event (SAE), serious adverse reaction (SAR) or unexpected serious adverse reaction	 Any adverse event, adverse reaction or unexpected adverse reaction, respectively, that: results in death, is life-threatening, requires hospitalisation* or prolongation of existing hospitalisation, results in persistent or significant disability or incapacity, or consists of a congenital anomaly or birth defect
Important Medical Event	These events may jeopardise the subject or may require an intervention to prevent one of the above characteristics/consequences. Such events should also be considered 'serious'.
Unexpected adverse reaction	An adverse reaction the nature and severity of which is not consistent with the information about the medicinal product in question set out: (a) in the case of a product with a marketing authorization, in the summary of product characteristics for that product, (b) in the case of any other investigational medicinal product, in the
SUSAR	investigator's brochure relating to the trial in question. Suspected Unexpected Serious Adverse Reaction

*Expected events relating to SPMS resulting in hospitalisation including Grade 3 relapses will not meet the criteria of an SAE in this trial. See sections 10.4.6 and 10.4.6.1.

10.2 DETECTING AEs AND SAEs

All AEs will be recorded in the medical records from the time a participant signs the consent form to take part in the study until study exit (Week 100).

Participants will be asked about the occurrence of AEs/SAEs at every visit during the study. Open-ended and non-leading verbal questioning of the participant will be used to enquire about AE/SAE occurrence. Participants will also be asked if they have been admitted to hospital, had any accidents, used any new medicines or changed concomitant medication regimens. AE data is also available from information written by the participant on the participant diary (this is considered source data). If there is any doubt as to whether a clinical observation is an AE, the event will be recorded.

AEs and SAEs may also be identified by support departments e.g. laboratory values.

10.3 RECORDING AEs AND SAEs

Collection, recording and reporting of adverse events (including serious and non-serious events and reactions) to the sponsor will be completed according to the sponsor's SOP(INV/S05).

When an AE/SAE occurs, it is the responsibility of the Investigator to review all documentation (e.g. hospital notes, laboratory and diagnostic reports) related to the event. The Investigator will then record all relevant information on the AE log in the CRF and on the SAE form (if the AE meets the criteria of serious). However, if the AE is non-serious (see section 10.1 for serious criteria definition) or MS related (see section 10.4.6.1 for MS expected adverse events) these will remain in the source data (Medical records and Participant diary cards) only. Information to be

Sponsor No.12/0219 v7 Page **57** of **73** collected includes dose, type of event, onset date, Investigator assessment of severity and causality, date of resolution as well as treatment required, investigations needed and outcome.

Clinically significant abnormalities in the results of objective tests (e.g. laboratory variables) will also be recorded as adverse events on the AE log in the CRF, and if are not expected as part of disease or IMP, these will be recorded as unexpected.

All adverse events will be recorded with clinical symptoms and accompanied with a simple, brief description of the event, including dates as appropriate.

All adverse events will be recorded until 4 weeks after the last clinical visit (study exit, visit 10) All Serious Adverse Events will be reportable to the sponsor up to 30 days post last IMP administration.

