1.2.2.2 Riluzole

Is licensed for motor neurone disease/amyotrophic lateral sclerosis (MND/ALS) and has two modes of action of relevance to SPMS: reducing glutamate release and antagonism of voltage dependent sodium channels.

Clinical Trial: Phase IIa: 16 patients with Progressive MS were studied 1 year before treatment, followed by riluzole 50mg bd for 1 year.²² The primary outcome was the change in cervical spinal cord cross-sectional area. It showed a reduction from -2% (yr 1) to -0.2% (yr 2). In addition, the increase in T1 hypointense lesion load was reduced from 15% in year 1 to 6% in year 2; there was a reduction in whole brain parenchymal/intracranial volume from -1.0% (yr 1) to -0.7% (yr 2).

Dosing and Safety: 50mg bd for 1 year was well tolerated in this study. In other disease areas, a study of 959 ALS patients, demonstrated that it is well tolerated at 100mg/day, with the most frequent drug related events being nausea (12-21% riluzole vs 12% placebo) and fatigue (15-20% vs 12%). Dizziness, diarrhoea, anorexia and paraethesiae were also reported. Increased liver function tests (LFT) were observed in 10% of the 100mg group with an increase of \geq 5 upper limit of normal (ULN) leading to withdrawal in 4%. ALTs 3-5 ULN usually decreased to normal within 2-6 months of continuous treatment. In a separate study of 537 patients with Huntington's disease, studied over 3 years, it was well tolerated, with a total drug related drop-out rate of 6%. ²³

Dose justification: 50mg bd was the dose used in the MS trial above; it is also the standard dose in MND/ALS and will therefore be used for this trial.

Side-effects: In phase III clinical studies conducted in ALS patients treated with riluzole, the most commonly reported adverse reactions were asthenia, nausea and abnormal liver function tests. Other common minor side-effects are: headache, dizziness, paraesthesiae, somnolence, diarrhoea,

Sponsor No.12/0219 v7 Page **22** of **73** abdominal pain, vomiting, tachycardia. Rare serious side-effects were: neutropenia and interstitial lung disease.

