10.4.3 Assessment of Severity

The Investigator will make an assessment of severity for each AE/SAE and record this on the CRF or AE form according to one of the categories described in Table C:

TABLE C: ASSESSMENT OF SEVERITY OF AE/SAE						
The Investigator will make an assessment of severity for each AE/SAE and record this on the CRF or AE form according to one of the following categories:						
Category	Definition					
Mild	The adverse event does not interfere with the volunteer's daily routine, and does not require intervention; it causes slight discomfort					
Moderate	The adverse event interferes with some aspects of the volunteer's routine, or requires intervention, but is not damaging to health; it causes moderate discomfort					
Severe	The adverse event results in alteration, discomfort or disability which is clearly damaging to health					

Note: the term 'severe', used to describe the intensity, should not be confused with 'serious' which is a regulatory definition based on participant/event outcome or action criteria. For example, a headache may be severe but not serious, while a minor stroke is serious but may not be severe.

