10.4.6 Non Reportable AEs/SAEs/SARs

The following will not be reported on the AE log in the CRF or to the sponsor as AEs/SAEs/SARs

10.4.6.1 Expected events related to SPMS:

SPMS is a progressive neurological condition and as such deterioration in neurological symptoms is expected. Therefore natural changes in motor, sensory, balance, sphincter (including urinary tract infections), visual, cognitive and fatigue levels are excluded as AEs/SAEs/SARs and will not be reported as such. In addition, relapses will not be counted as AEs/SAEs/SARs, but will be collated separately. They will be graded as follows (and see appendix 4):

Grade 1 relapse: relapse not treated with corticosteroids

Grade 2 relapse: relapse treated with corticosteroids, but not requiring hospitalisation Grade 3 relapse: relapse treated with corticosteroids and requiring in-patient hospitalisation; or relapse not treated with corticosteroids but requiring in-patient hospitalisation

If the participant feels they are experiencing a relapse, they should contact their local MS team (nurse/consultant) or General Practitioner as per routine practice, so that appropriate management can occur. They should also inform the MS-SMART team at their next scheduled visit, so that the relapse can be documented as per appendix 4. At the Investigator's/nurse's discretion the patient can attend for an unscheduled visit, see section 7.

If however, the investigators suspects that the disease has progressed faster due to the administration of the IMP, then they will report this as an unexpected adverse event (important medical event) to the sponsor.

All laboratory values will be recorded on the appropriate pages of the CRF. When there is a shift of a solitary, or group of values during the course of the study, which in the opinion of the Investigator may be classed as serious (life-threatening) and may or may not be deemed

> Sponsor No.12/0219 v7 Page **60** of **73**

attributable to the medication, this finding must be notified to the sponsor immediately. In these instances, the patient will be treated appropriately without regard to the confines of the protocol.

Full details of contraindications and side effects that have been reported following administration of the IMP can be found in the relevant Summary of Product Characteristics (SmPC).

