Participants will be instructed to contact their Investigator at any time after consenting to join the trial if any symptoms develop. All adverse events (AE) that occur after joining the trial must be reported in detail in the Case Report Form (CRF) or AE form. In the case of an AE, the Investigator should initiate the appropriate treatment according to their medical judgement. Participants with AEs present at the last visit must be followed up until resolution of the event.

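### Section 10.3 contradicts itself, 10.4.3 and the close of 10.4.6.1 on whether non-serious adverse events enter the CRF, so their capture may depend on the site

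*Protocol*

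**What the plan says.** Section 10.3 gives an instruction and then takes most of it back. The instruction is: "The Investigator will then record all relevant information on the AE log in the CRF and on the SAE form", with the SAE form applying only if the event is serious. The next sentence opens "However, if the AE is non-serious (see section 10.1 for serious criteria definition) or MS related" and concludes that "these will remain in the source data (Medical records and Participant diary cards) only". Later in the same section, clinically significant laboratory abnormalities "will also be recorded as adverse events on the AE log in the CRF".

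Two other places carry no such limit:

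- Section 10.4.3: "The Investigator will make an assessment of severity for each AE/SAE and record this on the CRF or AE form". Its Table C includes a mild grade for events that need no intervention.
- Closing text of section 10.4.6.1: "All adverse events (AE) that occur after joining the trial must be reported in detail in the Case Report Form (CRF) or AE form".

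Section 10.4.6.1 separately states that "natural changes in motor, sensory, balance, sphincter (including urinary tract infections), visual, cognitive and fatigue levels are excluded as AEs/SAEs/SARs". That is a different rule, about natural change in SPMS.

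**The concern.** Most of the symptomatic reactions that section 1.2.2 lists for the three drugs would normally be non-serious:

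- fluoxetine: nausea, headache, insomnia and diarrhoea;
- riluzole: nausea, dizziness and headache;
- amiloride: nausea, abdominal pain and rash.

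If these events stay in local notes, they are not in the database from which the Data Monitoring Committee's unblinded safety review (9.2.5) and the final report are drawn. Section 10.4 also lets the Chief Investigator upgrade an AE to an SAE, which is hard to do for events that never leave the site.

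A statistical analysis plan cannot repair this, because it can only tabulate what has been entered. If some sites follow one sentence and some the other, the reported AE rates would partly reflect site practice.

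**Working it through.** The plan gives no figure on this point, so the main check sets the texts side by side.

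**1. Does a non-serious AE go on a trial form?**

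| Place | Rule | Non-serious AE on CRF or AE form? |
|---|---|---|
| 10.2 | All AEs go in the medical records, from consent to week 100 | Not stated |
| 10.3, opening | The sponsor's SOP governs both serious and non-serious events | Implied; the SOP is not shown |
| 10.3, instruction | AE log, plus SAE form if serious | Yes |
| 10.3, next sentence | Medical records and diary cards only | No |
| 10.3, laboratory text | Clinically significant abnormalities go on the AE log | Yes |
| 10.4.3 | Severity of each AE/SAE, including mild, goes on the CRF or AE form | Yes |
| 10.4.6.1, closing text | All AEs go in the CRF or AE form | Yes |

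**2. Can the sentences be reconciled as written?**

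- The carve-out might be meant only as relief from SAE reporting. It does not say so: it names the two source records and adds that the events stay there alone.
- It might be meant only for events that are both non-serious and MS related. The text joins the two with *or*, and each has its own cross-reference (10.1 and 10.4.6.1).
- The AE form in 10.4.3 and 10.4.6.1 might be something other than the CRF. It would still be neither a medical record nor a diary card.

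No reading satisfies all the sentences.

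**3. What reaches the database under each rule?**

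| Event type | 10.3 carve-out followed | 10.4.3 and 10.4.6.1 followed |
|---|---|---|
| SAE not exempted by 10.4.6.1 | Yes | Yes |
| Laboratory values (all on CRF pages, 10.4.6.1) | Yes | Yes |
| Clinically significant laboratory abnormality, on AE log | Yes | Yes |
| Non-serious symptomatic event | No | Yes |

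Only the last row changes.

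**4. Scale, using nausea on riluzole.** Nausea is a clean example because 10.4.6.1 does not touch it. Inputs are 440/4 = 110 per arm (9.1.1) and ALS rates of 12-21% on riluzole against 12% on placebo (1.2.2.2). Carrying those rates over to SPMS is an assumption.

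- Placebo: 110 × 0.12 = 13.2 patients.
- Riluzole: 110 × 0.12 = 13.2 to 110 × 0.21 = 23.1 patients.
- Excess: 0 to 9.9 patients.
- At 21% against 12%, SE = √(0.12 × 0.88/110 + 0.21 × 0.79/110) = 0.0497. The 95% interval is 9 ± 1.96 × 4.97 points, or about −1 to +19 points. Power at two-sided 5% is about 44%.

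**5. Effect of partial capture.** The documents do not say what fraction c of events would be entered. Suppose c is the same in both arms. The upper-end counts become 23.1c and 13.2c, so the excess is 9.9c: 9.9 patients at c = 1, 4.95 at c = 0.5, none at c = 0. The ratio stays at 0.21/0.12 = 1.75 for any c above 0.

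**The case against.** **The exclusion is not settled.** The opening of 10.3, its log instruction, 10.4.3 and the close of 10.4.6.1 all point towards capture. This stands. A reader might infer that the trial cannot compare the drugs' main known reactions with placebo. The documents do not support that: it would need every site to follow one sentence and ignore the others. Abnormal liver function tests on riluzole and hyperkalaemia on amiloride, both prominent known reactions, reach the CRF either way.

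**Under-recording should be similar across arms.** The trial is blinded and site is a minimisation variable (5.5.1), so relative risks should be roughly preserved. This also stands. Step 5 shows the loss falling on counts and absolute differences, and with them precision. A bias in the relative comparison is not shown.

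**Even full capture would give an imprecise comparison.** True: power is about 44% at the upper nausea rate. But AE tables are read for incidence and pattern as well as significance, and low power is no reason to lose events.

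**Section 10.4.6.1 is a reasoned choice.** A reader might infer that it removes drug-induced fatigue, so that the 3.3 to 8.8 excess fatigue patients implied by the ALS rates (110 × 0.03 to 110 × 0.08) would go unrecorded. That would happen only if every such case were labelled natural SPMS change. Section 10.2 says to record when in doubt, though not specifically on the CRF. Section 10.4 has causality judged as if the participant were on active drug. Fatigue is also measured by the NFI at baseline, week 48 and week 96 and compared with placebo (7.2, 9.2.4). The NFI is not an AE incidence and can miss early, transient fatigue, but logging every natural change has its own cost in noise. The objection succeeds on this part.

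**Conclusion.** The point holds as an internal contradiction. Section 10.3 conflicts with itself, with 10.4.3 and with the closing text of 10.4.6.1 on whether non-serious AEs enter the CRF. Where the carve-out is followed, non-serious symptomatic reactions cannot be tabulated by arm; where sites differ, capture is site-dependent. SAEs and laboratory reactions are unaffected.

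The number of events lost cannot be derived from the protocol. It depends on which sentence each site followed, so it ranges from none to all non-serious symptomatic events. The nausea figure of 0 to 9.9 excess patients per 110 shows the order of magnitude at risk for one reaction to one drug, if ALS rates carry over to SPMS. The conclusion does not extend to the natural-change exclusion in 10.4.6.1. Nor does it extend to balance symptoms, since section 1.2.2 names no balance reaction for any drug (dizziness on riluzole is the nearest).

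**What to change.** Delete the non-serious limb of the carve-out in 10.3 and state that every AE not exempted by 10.4.6.1 goes on the AE log in the CRF. That brings 10.3 into line with 10.4.3 and the closing text of 10.4.6.1. The MS-related limb, with its pointer to 10.4.6.1, can stay.

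Before database lock, enter the non-serious events that so far exist only in source notes. Section 10.2 already requires all AEs in the medical records, so the material should be there.

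The cost is a wording change, more log entries per participant and some retrospective data entry. The last item is not trivial: section 1.2.2.1 says recruitment is complete, this version is dated June 2018, and the synopsis ends the trial on 31.10.2018. Sites that used the carve-out throughout may have up to about two years of events per participant to enter.
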